1.4.2 Technetium-based radiotracers can detect TTR-CA without the need for an amyloid biopsy

[figure not shown]
Guidelines have been established for formalizing the diagnosis of amyloidosis, requiring a biopsy of tissue delineating the presence of amyloid in either the heart or another organ.⁶⁹ Unfortunately, for a significant percentage of patients with TTR-CA, more easily performed biopsies, such as fat pad biopsies have a low yield.⁵⁶ The performance of endomyocardial biopsy has been restricted to large centers with significant expertise, not only in the performance of the biopsy, but also in the pathologically evaluation of the type of amyloid, which is critical to accurate diagnosis and appropriate treatment. Our own single center data has shown that ^{99m}Tc-PYP imaging has a sensitivity and specificity for detecting TTR cardiac amyloid from either ATTRwt or Val122Ile and differentiation from AL in of 97% and 100% of patients, respectively with an area under the curve of 0.997.⁷⁰ More recent multicenter data with ^{99m}Tc-PYP imaging from Columbia University, Boston University and the Mayo Clinic evaluated the utility of this non-invasive approach to diagnose TTR-CA without the need for endomyocardial biopsy⁷¹. Cardiac retention of ^{99m}Tc-PYP was visually scored using the ratio of myocardial uptake to the contralateral chest (the H/CL: heart contralateral ratio), which when >1.5 had a very high sensitivity (90%) and specificity (92%) for identifying the subjects with TTR-CA. Additionally, an even larger international collaboration employing ^{99m}Tc-DPD, ^{99m}Tc-PYP or ^{99m}Tc-HDP imaging; using the following grading system; Grade 0 – absent cardiac uptake; Grade 1 – mild uptake less than bone, Grade 2 - moderate uptake equal to bone; Grade 3 - uptake greater than bone, has demonstrated that the vast majority of subjects with biopsy proven WT TTR (89.5%) or Val122Ile TTR (97.6%) demonstrated grade 2/3 uptake indicative of TTR-CA. Among subjects who had grade 2/3 uptake using either of the three isotopes and no monoclonal protein (as evident by serum protein electrophoresis with immunofixation without a monoclonal band and free light chain ratio that was between 0.26 or 1.65), the specificity of nuclear scintigraphy for identifying TTR-CA (compared to AL, hypertrophic cardiomyopathy, HFpEF from hypertension or another infiltrative disease) was 100%!⁷² *These data demonstrate that TTR-CA can be reliably diagnosed in the absence of histology and these data serve as the basis for employing this non-invasive test to evaluate subjects at risk for TTR-CA in the SCAN-MP trial⁷³.*

1.4.3 Myocardial retention of Tc99-PYP is prognostic in TTR-CA

In a retrospective, cohort study⁷¹ of 196 subjects with heart failure at 3 academic medical centers (Columbia University Medical Center, Boston University Medical Center and the Mayo Clinic) we evaluate cardiac retention of ^{99m}Tc-PYP using a quantitative heart-to-contralateral (H/CL) ratio. H/CL was calculated as total counts in a region of interest (ROI) over the heart divided by background counts in an identical size ROI over the contralateral chest. The outcome measured was time to death after ^{99m}Tc-PYP scan. Among the 144 subjects with TTR cardiac amyloid (the majority of who had ATTRwt [n=72] or the Val122Ile mutation ([n=24])), univariate analysis shown in Table 2 demonstrated that the H/CL >1.6 predicted worse survival (hazard ratio (HR) 4.273, 95% CI 1.27–14.37, P=0.02). In multivariate analysis encompassing age, gender, race, TTR mutation, NYHA class, troponin, BNP and eGFR, the HR for the H/CL ratio of >1.6 was still significant 6.2, 95% CI 1.5-30.4,

$p=0.0043$). In Kaplan-Meier analysis over a 4-year follow-up, survival was significantly worse if H/CL was >1.6 vs. <1.6 ($P=0.0029$ log-rank test). As shown in Figure 3, only 4 of 44 subjects (9.7%) with a H/CL < 1.6 died over the follow-up period while 32 deaths occurred in the cohort with a H/CL ratio of > 1.6 (35% mortality). Thus, not only can ^{99m}Tc -PYP imaging diagnose ATTR-CA without a biopsy (irrespective of genotype), but this approach has prognostic significance. These data collectively suggest that ^{99m}Tc -PYP scans can

Figure 3

relied upon in the proposed SCAN-MP study.

Table 2
Cox Proportional Hazards Univariable and Multivariable Predictors of Death Among Subjects with ATTR-CA^a

	N	HR	95% CI	P Value
Univariable				
Age, y	132	1.073	(1.017-1.132)	0.0102
Modified BMI ^b , kg dl/m ² g	129	0.974	(0.954-0.994)	0.0132
Male sex	132	1.111	(0.330-3.737)	0.8653
Black race	132	1.493	(0.634-3.513)	0.3589
ATTR mutation	132	0.827	(0.365-1.872)	0.6479
NYHA class, I-IV	110	5.232	(1.759-15.562)	0.0029
Troponin I ≥ 0.25 , ng/ml	104	4.054	(1.812-9.072)	0.0007
BNP ≥ 500 , pg/ml	108	2.896	(1.143-7.341)	0.0250
eGFR < 60 , ml/min	132	3.312	(1.445-7.592)	0.0047
LVEF < 45 , %	129	1.430	(0.640-3.193)	0.3835
H/CL Ratio ≥ 1.6	132	4.273	(1.271-14.370)	0.0189
Multivariable				
Model 1 ^c	132	6.1939	(1.500-30.368)	0.0043
Model 2 ^d	110	4.099	(1.045-16.083)	0.0431
Model 3 ^e	101	4.383	(0.984-19.515)	0.0525
Model 4 ^f	5	4.460	(1.167-17.042)	0.0288

Abbreviations: HR, hazards ratio; CI, confidence interval; BMI, body mass index; ATTR, transthyretin cardiac amyloid; NYHA, New York Heart Association; NT pro-BNP, amino-terminal pro-B-type natriuretic peptide; BNP, brain natriuretic peptide; eGFR, estimated glomerular filtration rate; LVEF, left ventricular ejection fraction; LA, left atrium; IVSD, interventricular septal thickness at diastole; MCF, myocardial contraction fraction; H/CL, heart-to-contralateral.

Model 1: H/CL Ratio > 1.6 adjusted by [age, male sex, black race, ATTR mutation].
 Model 2: H/CL Ratio > 1.6 adjusted by [age, male sex, black race, ATTR mutation, NYHA class].
 Model 3: H/CL Ratio > 1.6 adjusted by [age, male sex, black race, ATTR mutation, NYHA class, troponin I > 0.25 , BNP > 500 , eGFR < 60].
 Model 4: H/CL Ratio > 1.6 adjusted by [age, male sex, black race, ATTR mutation, NYHA class, troponin T $> 0.0.02$, NT pro-BNP > 2000 , eGFR < 60].

identify ATTR-CA early, enhance diagnostic accuracy and can provide prognostic information. Accordingly, the use of such radiotracer imaging is a major advance in the field of cardiac amyloid which is being incorporated into clinical algorithms⁷³ and is being

1.4.4 Myocardial Contraction Fraction (MCF) to identification and prognosticate in TTR-CA

We previously described the MCF⁷⁴, defined as the ratio of LV stroke volume to myocardial volume and demonstrated that the MCF could successfully distinguish patients with HFpEF from athletes with physiologic hypertrophy and normal controls. The MCF provided a measure of ventricular function independent of chamber size that represents a volumetric measure of abnormal myocardial shortening, which was able to distinguish physiologic from pathologic hypertrophy. Measures of LV chamber performance are based on the premise that the myocardium is nearly incompressible and does not change volume significantly from end-diastole to end-systole.⁷⁵ Capitalizing on this fundamental principle of the incompressibility of the myocardium and by indexing the stroke volume to the myocardial volume, the MCF is an index of the volumetric shortening of the myocardium. During systole, the myocardium shortens and thickens, reducing its contained volume by the stroke volume. The MCF, though operationalized prior to the advent and widespread measurement of strain using echocardiography, is highly correlated with global longitudinal strain.⁷⁶ MCF is analogous to ejection fraction (EF) in that is a ratiometric measure that is easily obtainable, unit less and therefore does not need to be indexed to body size, age or gender. We have shown in a small cohort with cardiac amyloid in whom the average EF was preserved (51.2% \pm 13.1) while the MCF was significantly decreased (29.9% \pm 15.8) and was an independent predictor of survival.⁷⁷ Similar prognostic ability was

confirmed by colleagues at the Mayo Clinic in AL amyloid⁷⁶ and by colleagues in London.⁷⁸ More recently, the prognostic capacity of MCF was confirmed in TTR cardiac amyloidosis in the Transthyretin Amyloidosis Outcomes Survey (THAOS).⁷⁹ Classically, the voltage to mass ratio (V/M) has been employed to identify the phenotype of CA, but its use is confounded by the fact that many elderly patients with amyloid have a paced rhythm, making calculation of the V/M ratio impractical. Preliminary data demonstrates that the MCF with an area under the curve of 0.773 (p<0.0002, 95% CI 0.66–0.86) for identifying TTR-CA was similar to the V/M ratio with an AUC of 0.678 (p=0.07, 95% CI 0.54–0.79). *Accordingly, the MCF has potential as a simple measure to raise suspicion of TTR-CA as well as informing prognosis.*

1.4.5 A method to quantify TTR kinetic stability

In collaboration with [name] and colleagues at Scripps, we have been studying the structure, energetics and dynamics of WT and mutant TTR in human plasma, towards development of mechanisms to identify individuals susceptible to TTR-CA and predict clinical benefit in treating TTR-CA. Using a published subunit exchange method for quantifying the kinetic stability of human TTR in plasma, we were able to demonstrate that tafamidis kinetically stabilizes TTR and that the extent of TTR kinetic stabilization correlated with the tafamidis plasma concentration.⁸⁰ Additionally, using this simple assay carried under physiological conditions, we were able to optimize the dose of tafamidis in a patient's plasma to maximize TTR kinetic stability.⁸¹ We hypothesize that by studying the kinetic stability of WT TTR in plasma, that we can identify those at risk for developing TTR-CA (see below).

2. STUDY OBJECTIVES & STUDY DESIGN

2.1 Primary Objective

To enhance the understanding of genotype-phenotype associations in Blacks/ Hispanics with ATTR-CA due to the Val122Ile mutation or ATTRwt and to improve identification of minority patients with ATTR-CA.

2.1.1 Research Goal

The goal of our research is to change the approach to transthyretin cardiac amyloidosis, which is a devastating disease, by screening and early diagnosis, and by studying prospectively a cohort of older Blacks/Hispanics with heart failure in order to address the following aims and hypotheses:

Specific Aim 1: To determine the prevalence of ATTR CA in Caribbean Hispanics and Blacks with HF. The hypotheses to be tested include:

- (1) the prevalence of ATTR CA will be 10-15%
- (2) ATTRwt CA will be higher among Caribbean Hispanics compared to US Blacks, whereas the prevalence of ATTRm CA will be lower
- (3) the gender distribution of ATTR CA identified by this active ascertainment approach will be similar
- (4) disease progression will demonstrate that ATTRm is associated with a more rapid decline vs. ATTRwt
- (5) the accuracy of our clinic-based risk calculator will be confirmed in this large prospectively recruited cohort

Specific Aim 2: To demonstrate that circulating RBP4 concentration is integral to TTR tetramer stability which in turn determines the clinical characteristics of ATTR CA. We will measure TTR tetramer stability and RBP4 concentration in serum and urine collected in Aim 1. The hypotheses to be tested include:

- (1) TTR tetramer stability will be lower in ATTR CA and directly relate to RBP concentration
- (2) TTR tetramer stability will associate with clinical features and
- (3) Increased renal clearance of RBP4 in ATTR CA will be determined by measurement of RBP4 in plasma and urine.

2.1.2 Overview of Study Design

We will undertake a prospective cohort study among outpatient subjects with heart failure seen at one of five sites: (1) Columbia University Medical Center, (2) Allen Hospital of NY Presbyterian, (3) Harlem Hospital, (4) Boston University/Boston Medical Center and (5) Yale New Haven Hospital.

Black/Hispanic subjects over the age of 60 years with heart failure will undergo comprehensive cardiovascular examinations including: (1) complete medical history documenting the presence of HF and any symptoms that could be associated with TTR amyloidosis, as well as any additional co-morbid conditions or symptoms, (2) targeted physical exams including orthostatic blood pressure measurements, assessment for gallops and volume status (e.g. JVP, rales, edema) and determination of functional class, (3) standard 12 lead electrocardiogram, (4) measurement of plasma N-terminal B-type natriuretic peptide, troponin T and I RBP, Vitamin A and TTR kinetic stability, (5) RBP in urine, (6) six minute hall walks and (6) full two-dimensional and three-dimensional echocardiograms with Doppler flow assessment and tissue Doppler and speckle tracking (See procedures for details), (7) ^{99m}Tc-PYP or ^{99m}Tc-HMDP scintigraphy and (8) genetic analysis for the Val122Ile mutation in all subjects in a CLIA lab.

2.1.3 Patient Recruitment

The SCAN- MP study is designed to identify a sufficient number of cases to support the following analytical objectives:

1. Stratify prevalence of ATTR-CA in subjects with HF by relevant demographic characteristics (gender, race/ethnicity, genotype); and
2. Evaluate relationships among ATTR-CA and baseline risk factors (presence of Val122Ile mutation and others) with disease outcomes.

To accomplish these objectives, a hybrid approach to cohort identification and selection is used that combines deliberate selection of subjects with heart failure who are at increased risk for ATTR-CA and selection of participants with relevant characteristics (age, gender, race/ethnicity, country of origin). Planned proportion of enrolled subjects by relevant characteristics is shown in the Table 3. Community involvement is essential for its success and recruitment will involve intensive community engagement through various means among the sites. In aggregate, we will recruit an equal number of men and women from the racial/ethnic groups. The expected marginal distributions of race/ethnicity are shown in Table 3. We will have overlapping ethnic groups among centers to minimize confounding of ethnicity by site. As recruitment of elderly members of minority groups is challenging, toward end of the recruitment period, participants will be asked to refer elderly persons to the study.

Table 3. Planned Enrollment by Age, Race, and Gender

Age (yr)	Black		Hispanic or Latino ethnicity		Total	
	M	F	M	F	M	F
≤75	150	150	50	50	200	200
>75	150	150	50	50	200	200

At CUMC we have seen 24,682 unique patients with HF over the last five years of which 2,969 (12%) self-identified as Black and 4,387 of 14,466 (29.9%) patients who declared their ethnicity were Hispanic and whose average age was 63 years. Harlem Hospital provides health care services to the primary service area of Harlem, Washington Heights/Inwood and the South Bronx with the vast

majority of residents being African American (44.5%) and Hispanic (40.8%). Thus, there are ~1500 potential subjects per year from which we aim to recruit at least 100 subjects per year at the CUMC site. For the Boston site, we propose to recruit an equal number of participants with similar demographic distribution. The overall patient population at Boston Medical Center is ethnically diverse with 39% Black and 15% Hispanic of all patients seen. A preliminary assessment of recruitment feasibility suggests that ~750 patients are seen annually with HF who are Black or Hispanic.

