Inclusion and Exclusion Criteria	
Every participant must meet all of the following inclusion criteria to be eligible for enrollment in this study:
 
 1. Black or Hispanic of Caribbean origin. 2. Age ≥ 60 years. 3. Diagnosis of heart failure, confirmed by one of two methods: 
 a. Modified criteria utilized by Rich et al. which include a history of acute pulmonary edema or the occurrence of at least two of the following that improved with diuretic therapy without another identifiable cause: dyspnea on exertion, paroxysmal nocturnal dyspnea, orthopnea, bilateral lower extremity edema or exertional fatigue, and

	
b. NHANES CHF criteria with a score ≥ 3 (see Appendix 1).
 
 4. Left ventricular septal OR inferolateral wall thickness ≥ 12 mm. 5. Ejection fraction $> 30\%$. 6. Able to understand and sign the informed consent document after the nature of the study has been fully explained. 
The presence of any of the following excludes eligibility for enrollment in this study:
 
 1. Primary amyloidosis (AL) or secondary amyloidosis (AA). 2. Prior liver or heart transplantation. 3. Active malignancy or non-amyloid disease with expected survival of less than 1 year. 4. Heart failure, in the opinion of the investigator, primarily caused by severe left-sided valve disease. Note: if valve was repaired, subject may be considered as no longer with severe valve disease. 5. Heart failure, in the opinion of the investigator, primarily caused by ischemic heart disease. 6. Ventricular assist device or anticipated within the next 6 months. 7. Impairment from stroke, injury or other medical disorder that precludes participation in the study. 8. Disabling dementia or other mental or behavioral disease. 9. Enrollment in a clinical trial not approved for co-enrollment. 10. Expected use of continuous intravenous inotropic therapy in the next 6 months. 11. High risk for non-adherence as determined by screening evaluation. 12. Inability or unwillingness to comply with the study requirements. 13. Chronic kidney disease with eGFR < 15 mL/min/1.73 m² or ESRD. 14. Weight > 350 lb. 15. Nursing home resident. 16. Other reason that would make the subject inappropriate for entry into this study.

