Pressure-Volume Relations (upper panel) and iso-volumetric pressure-volume area (PVA-iso, lower panel): Baseline to 18-month follow-up (left panel), V122I versus Wild-Type at baseline (middle panel) and Survivors versus Non-survivors (right panel). There were significant (e.g. $p < 0.05$) increases in Ea, declines in Res and altered Ea/Res ratio from baseline to 18 months (right panel) as well as differences in baseline in Ea and Ea/Res ratio between wild-type and V122I (middle panel) as well as between survivors and non-survivors (right panel). Additionally, significant differences in PVA-iso curves were noted for all three comparisons.

These data show that subjects with Val122Ile had a more severe phenotype with a reduced ability of the ventricle to perform work. This could be due a more malignant course among subjects with the Val122Ile mutation compared to the ATTRwt genotype or are due to later presentation among the Blacks with Val122Ile than among ATTRwt subjects, as a result of racial disparities resulting in poor access to care. Accordingly, using such measures in a larger and unselected cohort of Blacks/Hispanics with both forms of TTR-CA, identified by cardiac amyloid scanning, we can evaluate the physiologic effect of the amyloid infiltration in those with and without a genetic cause. Thus, we can determine the true impact of the genotype on the phenotype and on outcomes in Blacks/Hispanics from the same geographic and socio-economic region.

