2.1.6 Hypotheses

Aim 1: To determine the prevalence of ATTR CA in Caribbean Hispanics and Blacks with HF

Hypothesis 1. Overall prevalence of ATTR CA: The prevalence of ATTR CA will be defined by the number of cases with both ATTRwt and ATTRm CA as a percentage of total enrollment. The background prevalence of Val122Ile in the US Black population is 3.4%, and we hypothesize a prevalence rate of 8% of ATTRm Val122Ile in our outpatient HF population. Since there are no data in Hispanics regarding ATTR CA prevalence, we further hypothesize that we will observe a prevalence of ATTRwt CA of 2-8% of the Hispanic population. Thus, we have conservatively defined the predicted prevalence of ATTR CA as 10-15%.

Hypothesis 2. Relative proportion of ATTR CA comprised by ATTRwt and ATTRm: As noted above, based upon the background allele frequency, we anticipate that Black patients will be much more likely to manifest ATTRm (Val122Ile) vs. ATTRwt CA, whereas Hispanic patients will be more likely to manifest ATTRwt CA. We will be able to explore the Val122Ile genotype frequency in the Hispanic population, and with the addition of cardiac amyloid scintigraphy scanning, the relative contribution of ATTRm in this population, which we postulate to be lower than Blacks. We will utilize genetic ancestry analysis data to further characterize race and ethnicity, and, as an exploratory analysis, evaluate the interaction of genetic variants identified with Val122Ile and ATTR CA as defined by radiotracer uptake.

Hypothesis 3. Proportion of gender: Published reports of ATTR Val122Ile are 75% male and reports of ATTRwt are 95% male. We hypothesize that highly sensitive cardiac amyloid scintigraphy testing will reveal a gender distribution of ATTR that is closer to 50%, based upon allele distribution. We will explore comorbidities, TTR stability, and RBP4 differences among men and women with ATTR to determine interactions with phenotypic expression.

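### If selection for increased ATTR-CA risk goes beyond the eligibility criteria, the raw Aim 1 prevalence is likely overstated, and neither the planned analysis nor the forms would show by how much

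*Combined protocol and SAP*

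**What the plan says.** Aim 1 is the prevalence of ATTR-CA in Caribbean Hispanics and Blacks with heart failure (2.1.1, 2.1.6). Four parts of the combined protocol and SAP bear on what the estimate will mean.

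- **Who is approached.** Section 2.1.3 describes a hybrid approach. One component is "deliberate selection of subjects with heart failure who are at increased risk for ATTR-CA". The other is selection on age, gender, race/ethnicity and country of origin, with the planned numbers in Table 3. The section adds that "toward end of the recruitment period, participants will be asked to refer elderly persons to the study". It gives no definition of increased risk, no sampling fraction, and no rule for consecutive or random approach.
- **Who is eligible.** The synopsis excludes AL and AA amyloidosis. None of its 16 exclusions names ATTR, and 2.1.4 does not either.
- **How prevalence is estimated.** Section 2.1.6 counts wild-type and mutant cases "as a percentage of total enrollment". Section 2.1.8 uses sample proportions with exact 95% confidence intervals. No weighting, standardisation or sensitivity analysis is planned, and 2.2 does not discuss selection bias in the prevalence.
- **What is recorded.** The Appendix 4 screening, demographics and 28-item history forms have no field for recruitment source, prior amyloidosis, prior scan or known TTR genotype.

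Section 1.3.2, in contrast, speaks of "using such measures in a larger and unselected cohort of Blacks/Hispanics with both forms of TTR-CA".

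**The concern.** A sample proportion estimates population prevalence only if the chance of being enrolled does not depend on having the disease. The wording of 2.1.3 starts from heart failure patients and then selects those more likely to have ATTR-CA. If sites act on that, the outcome influences who enters the denominator. Hypothesis 1 predicts 10-15%, and that range could then be reached from a lower true prevalence through recruitment practice alone. The exact interval covers binomial sampling error only.

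There is ample room for selection. Section 2.1.3 cites about 1,500 potential subjects a year, with at least 100 a year to be recruited at the Columbia site. At that target about 1 in 15 is enrolled (1,500/100), with no rule for which one. Columbia and Boston also have established ATTR cohorts (1.2.3, 1.4.3).

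The age quota is a separate and better documented route. Half the cohort is to be over 75, and the protocol's own background data show a steep rise of cardiac amyloid with age.

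**Working it through.** **The plan's own figures.** With N = 800 (2.1.7) and 10-15% (2.1.6), the expected cases are 800 × 0.10 = 80 and 800 × 0.15 = 120. Section 2.1.7 gives 80-160 under Aim 1 and 80-120 under Aim 2. Only the second matches, since 160 needs 20%. The 80% power claimed for a prevalence of 10-15% cannot be checked, because no null value or precision target is stated.

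**Planned precision** (Clopper-Pearson):

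| Cases/800 | Estimate | Exact 95% CI |
|---|---|---|
| 80 | 10.0% | 8.0-12.3% |
| 100 | 12.5% | 10.3-15.0% |
| 120 | 15.0% | 12.6-17.7% |

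At 100/800 the half-width is (15.0 − 10.3)/2 = 2.35 points and the full width 4.7 points.

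**Selection on suspicion.** The documents give no rate, so these inputs are assumptions: true prevalence 10%, a fraction f of enrolment picked on suspicion, and a proportion p1 of those positive. Observed = (1 − f) × 0.10 + f × p1.

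| f | p1 = 30% | p1 = 50% |
|---|---|---|
| 5% | 0.095 + 0.015 = 11% | 0.095 + 0.025 = 12% |
| 10% | 0.09 + 0.03 = 12% | 0.09 + 0.05 = 14% |
| 20% | 0.08 + 0.06 = 14% | 0.08 + 0.10 = 18% |

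The shift is 1-2 points at f = 5%, below the half-width. It is 2-4 points at 10% and 4-8 points at 20%. Put another way, suppose a patient with ATTR-CA is k times as likely to be enrolled as one without. Then observed = k × 0.10/(k × 0.10 + 0.90), which is 12.2% at k = 1.25 and 14.3% at k = 1.5.

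**Over-sampled known cases.** Diagnosed patients in their natural proportion belong in a prevalence, so only an excess counts. Let m be that excess among 800: observed = (m + (800 − m) × 0.10)/800. For m = 10, 20 and 30 this gives 11.1%, 12.3% and 13.4%. These values of m are assumed; the documents give no count.

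**Age quota.** Table 3 plans 400 of 800 (50%) above age 75. Section 1.2.1 reports amyloid at autopsy in 20 of 63 (32%) HFpEF patients aged 75 or over at diagnosis, against 4 of 50 (8%) below 75. Apply these rates only as a gradient. At the quota, the crude rate is 0.5 × 32% + 0.5 × 8% = 20%. For an assumed source share s above 75:

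| s | 0.32s + 0.08(1 − s) | Ratio of 20% to this |
|---|---|---|
| 15% | 11.6% | 1.72 |
| 25% | 14.0% | 1.43 |
| 35% | 16.4% | 1.22 |

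The documents do not give s. They give only an average age of 63 for Columbia's Hispanic heart failure patients, a figure not limited to those aged 60 or over. Autopsy deposits are also not the same as a positive scan. The table therefore shows that the raw proportion depends on the quota, not by how much.

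**The case against.** The strongest reply is that increased risk in 2.1.3 may mean no more than the entry criteria: age 60 or over, "Left ventricular septal OR inferolateral wall thickness" of at least 12 mm, and heart failure not mainly ischaemic or valvular. Section 2.2 supports this when it describes the cohort with a sufficient chance of cases simply as those with heart failure. Section 2.1.2 recruits outpatients with heart failure at the sites. This stands as a possible reading, and it is why the bias is conditional. But 2.1.3 narrows from heart failure patients and lists the risk selection apart from demographics, so the text does not settle it.

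A reader might infer more than the documents support:

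- **That prevalence is shown to be inflated.** No text says that sites pick on suspicion, enrol known ATTR cases or recruit relatives. Some exclusions, such as prior transplant, nursing-home residence and enrolment in another trial, could remove cases.
- **That the effect cannot be recovered.** Age, sex, ethnicity and country of origin are recorded, so the quota effect can be standardised. Enrolment date approximates the late referral phase, and charts can supply much of the rest.
- **That eligibility of diagnosed ATTR is itself an error.** It is not; only over-sampling biases the result.
- **That referral brings in families at 50% carriage against a 3.4% background.** Referral is of elderly persons, who must still meet the criteria. The 3.4% is a general-population rate: 1.2.1 reports 10% carriage in Blacks over 60 with heart failure. Carriage is not disease, and 1.1.2 calls penetrance unknown. Any relatives who do enter would weaken the independence behind the exact interval.
- **That the Black-Hispanic contrast is distorted.** That would generally need selection that differs by ethnicity, and none is identified.

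The conflict with 1.3.2 is also mild: that sentence is background, contrasting the planned cohort with earlier clinical series.

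**Conclusion.** The point holds in conditional form. If 2.1.3 is followed as written and increased risk means more than the listed criteria, the Aim 1 estimate is likely too high for its stated population, and the exact interval will not show it. Under the assumed inputs, a true 10% reads as 11-18%. The low end lies within the half-width of about 2.35 points; the high end is well beyond it. Over-sampling of diagnosed cases would add to this. The direction is probable rather than demonstrated, and the size is unknown.

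The dependence on the age quota does not rest on how increased risk is read. It follows from Table 3, an unweighted estimator and any age gradient in ATTR-CA, provided the source population is not itself half over 75. It can be corrected with data already collected, plus the source distribution.

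**What to change.** 1. **Section 2.1.3.** Replace the risk-selection clause with a statement that, within each Table 3 cell, sites approach heart failure patients who meet the listed criteria without reference to amyloid suspicion. Alternatively, state that increased risk means only the listed criteria. Reconcile this with the description in 1.3.2.
2. **Screening form.** Add flags for prior ATTR diagnosis or bone-tracer scan; known TTR genotype; referral for suspected amyloid; and referral by, or blood relation to, a participant. Complete them from charts for those already enrolled.
3. **Section 2.1.8.** For hypotheses 1 and 2, report prevalence in all enrolled, and again without participants who entered through amyloid suspicion or participant referral. Show prior-diagnosed cases separately. Both versions are needed, because the restricted one drops genuine heart failure patients with ATTR-CA and may err downward. Add an estimate standardised by age, sex and ethnicity to the sites' heart failure population.
4. **Hypothesis 4 and Aim 2.** Keep all participants.

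The cost is some wording, a few form items, a one-time chart check and the source age, sex and ethnicity distribution from each site. The restricted analysis has a smaller denominator, and the headline prevalence will probably be lower. Ending risk-based approach may also yield fewer cases for hypothesis 4, whose power statement in 2.1.7 assumes 80 (40 per genotype group).
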